Another interesting aspect in relation to antimalarial is that the mechanism of its beneficial effect has not yet been fully clarified, but it is believed to be correlated with the blockade of toll-like receptors (TLR7-9) and inhibition of alpha interferon production, which plays a crucial role in the pathogenesis of SLE. In fact, an *in vitro* study observed that the use of hydroxychloroquine inhibits the production of interferon-alpha and TNF by plasmacytoid dendritic cells of patients with SLE and, apparently, this inhibition is more effective for TLR-9 than for TLR-7 (Sacre et al., 2012). However, there is still a need to determine the possible correlation between the level of antimalarial and the degree of inhibition of the two different receptors.

Objectives primary:

- Monitoring of HCQ blood levels: possible relevance on disease activity in JSLE and renal adult SLE to inclusion and 6 months following inclusion.

Secondary:

- Evaluate the predictive value of HCQ levels for JSLE disease activity and renal disease activity in adult SLE within 6 months of inclusion.

- To verify the possible association between blood levels of HCQ with adherence to treatment assessed by a specific questionnaire.

- Evaluate the correlation between blood and salivary levels of HCQ in a subgroup of patients with SLE and JSLE and their possible association with therapeutic response and safety.

- Check whether the production of interferon-alpha and TNF by plasmacytoid dendritic cells correlates with blood HCQ levels.

NUMBER OF INDIVIDUALS

Total patients required for the study = 309, being: SLE (n= 206), SLEJ (n= 103).

STUDY DESIGN

Initially, a cross-sectional study will be conducted with patients using HCQ at a dose of 5-6.5 mg/kg/day (maximum of 400 mg/day) for at least 6 months (Clark et al., 1993). At the entrance, peripheral blood samples will be taken to determine HCQ levels and patients will be evaluated for the activity of the underlying disease in a "blind" way to HCQ concentrations.

The following indices will be used to assess disease activity every 3 months:

- SLE and SLEJ: Systemic Lupus Erythematosus Disease Activity Index (SLEDAI-2K) (Gladman et al., 2002) and active disease randomly defined as SLEDAI-2K \geq 6.

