- Renal activity: blood pressure (BP), urine type I, protein and creatinine in an isolated urine sample, serum keratinize, C3, C4, anti-dsDNA, according to the recommendations of the American College of Rheumatology (ACR) (Hahnet et al., 2012).

Adherence will be evaluated by the Medication Adherence Self-report Inventory (MASRI) applied by a pharmacist not directly involved in patient care (Koneru et al., 2007).

SLE and JSLE: Systemic Lupus Erythematosus Disease Activity Index (SLEDAI-2K) (Gladman et al., 2002) and active disease randomly defined as SLEDAI-2K \geq 6.

- Renal activity: blood pressure (BP), urine type I, protein and creatinine in an isolated urine sample, serum creatinine, C3, C4, anti-dsDNA, according to the recommendations of the American College of Rheumatology (ACR) (Hahnet et al., 2012).

Adherence will be evaluated by the Medication Adherence Self-report Inventory (MASRI) applied by a pharmacist not directly involved in patient care (Koneru et al., 2007).

The production of interferon-alpha and TNF-alpha by plasmacytoid dendritic cells will be evaluated in vitro using mononuclear cell preparations isolated from peripheral blood from a random sample of the same number of consecutive patients with active and inactive SLE. The cells will be stimulated with the TLR-9 agonist, Oligodeoxynucleotides CpG (ODN CpG-A) -2216, and with the TLR-7 agonist, imiquimod. The percentage of monocytes, B cells, dendritic cells and natural killers (NK) in the PBMC fraction will be determined by the phenotypic characterization of these cell subpopulations by flow cytometry using monoclonal fluorochrome-conjugated antibodies. Intracellular detection of IFN-alpha and TNF-alpha in plasmacytoid dendritic cells will also be performed by flow cytometry and specific monoclonal antibodies (Sacre et al., 2012).

TARGET POPULATION

Inclusion criteria:

- LES and LESJ: Criteria of the American College of Rheumatology (ACR) (Hochberg, 1997);
- use of HCQ at a dose of 5-6.5 mg/kg/day (maximum 400 mg/day) for at least 6 months.

Exclusion criteria:

- alcoholism;
- renal dialysis;
- concomitant infectious process;
- acute and chronic liver diseases and
- concomitant use of some drugs that interact with HCQ (cimetidine, antacids, digoxin, aminoglycosides, penicillin, neostigmine, pyridostigmine).

RELEVANT METHODS

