Intracellular detection of IFN-alpha and TNF-alpha cytokines in plasmacytoid dendritic cells: PBMC cells will be stimulated with TLR-7 and TLR-9 agonists, imiquimod (5 µg/mL) and CpG-A ODN 2216 (5 µM) for 5 hours at 37°C. After 3 hours of stimulation, Brefeldin A will be added to induce the accumulation of cytokines in the endoplasmic reticulum by its inhibitory action on intracellular protein transport to the Golgi complex. Phenotypic cell characterization (PBMC) and intracellular detection of cytokines will be performed by sequential membrane marking and intracellularly using specific monoclonal antibodies labeled with fluorochromes followed by evaluation by flow cytometry (Sacre et al., 2012).

WITHDRAWALS

It doesn't apply.

ORIGINALITY WITH IMPACT

Healthcare

To date, there is no study that has evaluated blood and salivary levels of hydroxychloroquine (HCQ) and its predictive value for disease activity in JSLE and adult lupus nephritis.

The expected impact with the availability of this technique in clinical practice is an improvement in therapeutic adherence and an earlier intervention with reduction of outbreaks of disease activity. The use of saliva as an alternative to this monitoring would provide a less invasive technique for this process.

ADVANCES IN MECHANISMS

The expected progress is a better understanding of the mechanism of action of HCQ on TLR-7-9, previously suggested as possible therapeutic targets for the disease.

STATISTICAL PLAN

SAMPLE SIZE

The sample size was calculated based on the HCQ levels observed in the study by Costedoat-Chalumeau et al., 2006, in patients with SLE and assuming: 95% confidence interval, α error of 5%; power of 80%; mean HCQ concentration in active patients: 694 ± 448 ng/mL; mean HCQ concentration in inactive patients: 1079 ± 526 ng/mL; aggregate standard deviation: 532 ng/mL and loss: 10%.

For the SLE group with nephritis, 16% of SLE patients in our outpatient clinic present active renal disease, then we expect 33 patients with renal activity out of the 206 patients which will be included.

For the JSLE group, 34% of our outpatient clinic patients present active, then 35 with disease activity are expected out of a total number of 103 patients to be included statistical analysis. The groups of patients with and without disease activity will be compared for categorical variables by Fisher's exact test and, for quantitative variables, by student and mann-whitney t tests, when applicable.

TITLE OF THE

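### Subproject 1A: no analysis is specified for whether entry HCQ level predicts activity within 6 months, and the one test given can let entry activity pass for prediction

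*Combined protocol and SAP*

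**What the plan says.** The 1A objectives look forward in time. The primary objective concerns HCQ levels and their "possible relevance on disease activity in JSLE and renal adult SLE to inclusion and 6 months following inclusion". The first secondary objective is to "Evaluate the predictive value of HCQ levels for JSLE disease activity and renal disease activity in adult SLE within 6 months of inclusion".

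Under Study Design: "Initially, a cross-sectional study will be conducted with patients using HCQ at a dose of 5-6.5 mg/kg/day". HCQ is sampled at entry, and follow-up of activity is planned: "The following indices will be used to assess disease activity every 3 months". Activity is a current state, "active disease randomly defined as SLEDAI-2K" of 6 or more; renal activity is judged from a list of clinical and laboratory measures. No new episode or flare is defined.

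The inclusion criteria are ACR classification and "use of HCQ at a dose of 5-6.5 mg/kg/day (maximum 400 mg/day) for at least 6 months". Activity at entry is neither required nor excluded. The Sample Size section in fact expects active patients: 33 of 206 adults with renal activity and 35 of 103 JSLE patients.

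The analysis is one sentence at the end of that section: "The groups of patients with and without disease activity will be compared for categorical variables" by Fisher's exact test, and quantitative variables by t or Mann-Whitney tests. It states no grouping visit, no adjustment for entry activity, and no regression, time-to-event or discrimination measure.

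**The concern.** Prediction asks whether the level measured at entry tells us something about later activity that the patient's state at entry does not. A two-group comparison by activity status cannot answer that, whichever visit defines the groups. With groups formed at entry, it describes who is active now. With groups formed at 6 months, the active group contains patients who were already active when HCQ was measured. If levels are lower in patients who are currently active, as the plan's sample size assumes, those patients pull down the mean of the month-6 active group even when HCQ carries no further information.

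The objective is secondary, but 1A's section on originality and impact rests on predictive value and on earlier intervention to reduce outbreaks. The background also separates the two ideas, reporting low levels both as associated with activity and as a predictor of exacerbation over the next six months. The analysis does not keep that separation.

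**Working it through.** **1. The plan's own figure.** Inputs from the 1A Sample Size section: means 694 and 1079 ng/mL (difference 385), SD 532, alpha 5% (two-sided assumed), power 80%, loss 10%, clinic prevalence of activity 16% (adult renal) and 34% (JSLE).

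- Per group, normal approximation: 2 × [532 × (1.960 + 0.842) / 385]² = 29.97, so 30.
- Adults: 30 × 1.1 = 33 active; 33 / 0.16 = 206.
- JSLE: the t-test version gives 31; 31 / 0.9 = 34.4, so 35 active; 35 / 0.34 = 103.

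Both totals reproduce, with slightly different rounding and loss adjustment. They are sizes for currently active versus currently inactive patients. At these group sizes that contrast has about 97% (adult) and 94% (JSLE) power before losses. Nothing is sized for prediction.

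**2. Who is in the month-6 active group.** Persistence and incidence are not in the documents; 30-60% and 5-20% are assumed. Share already active at entry = persistent / (persistent + new). Inactive at entry: 206 − 33 = 173 adults; 103 − 35 = 68 JSLE.

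| Group | Persistence | Persistent | New (5% to 20%) | Share already active |
|---|---|---|---|---|
| JSLE | 60% | 35 × 0.6 = 21 | 3.4 to 13.6 | 86% to 61% |
| JSLE | 30% | 35 × 0.3 = 10.5 | 3.4 to 13.6 | 76% to 44% |
| Adult | 60% | 33 × 0.6 = 19.8 | 8.7 to 34.6 | 70% to 36% |
| Adult | 30% | 33 × 0.3 = 9.9 | 8.7 to 34.6 | 53% to 22% |

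**3. What the stated test would do.** The share is not itself the bias, so the test was simulated (4,000 runs per setting, 10% loss). HCQ was drawn from the plan's values, 694 ± 448 if active at entry and 1079 ± 526 if not, with no relation to later activity given entry status. Patients were grouped by month-6 activity and compared by t test. With persistence 30-70% and incidence 5-10%, p < 0.05 occurred in 12-68% of adult runs and 12-65% of JSLE runs instead of 5%, with an apparent deficit of about 93-286 ng/mL. Restricted to patients inactive at entry, the rate was about 4-6%. The inflation fades as persistence falls and incidence rises: at 30% and 20% the rate is close to nominal, about 6%.

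**4. What a restricted analysis would have.** At risk after 10% loss: 173 × 0.9 = 156 adults; 68 × 0.9 = 61 JSLE. The last columns give power for the plan's 385 ng/mL difference.

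| Incidence | New adults | New JSLE | Power, adults | Power, JSLE |
|---|---|---|---|---|
| 5% | 8 | 3 | 50% | 23% |
| 10% | 16 | 6 | 77% | 40% |
| 16% | 25 | 10 | 91% | 55% |
| 20% | 31 | 12 | 95% | 62% |

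Precision in JSLE is poor: an observed sensitivity of 2/3 has an exact 95% interval of 9-99%.

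**The case against.** A reader might infer that the plan *will* present entry activity as prediction. The documents do not support that. The grouping visit is not given; if groups are formed at entry, the predictive objective simply has no analysis and nothing is misreported.

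A reader might also infer that a month-6 comparison would largely repeat the cross-sectional association. That is not secure either. In adults at the low end only 22% of the active group would be carried over, and the false-positive rate can lie near nominal. The size depends on two rates that the documents omit.

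Three further points stand in part:

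- The objective speaks of activity, not new activity or flare. The background on exacerbation favours new activity, but the choice is the sponsor's.
- Low levels through poor adherence are not an artefact of the grouping. The background treats blood level as a marker of adherence, and 1A studies that association separately.
- The 1000 ng/mL level appears in 1A only as background from a cited study; 1A adopts no cut-off.

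The objective is also secondary, in a subproject titled cross-sectional and sized for that contrast. None of this supplies an analysis. The log-rank tests belong to 1B and 1C, and the multivariate analysis to the thalidomide project.

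**Conclusion.** The point holds in this form: 1A states a predictive objective and specifies no analysis that can meet it. Under entry grouping the objective goes unanswered. Under month-6 grouping persistent and new activity are mixed, and entry activity can pass for prediction. On assumed persistence of 30-60% and incidence of 5-20%, 44-86% of JSLE and 22-70% of adult patients active at 6 months would already have been active at entry. The resulting false-positive rate ranges from near nominal to more than half of simulated runs. That simulation also assumes normally distributed levels that differ by entry activity as the sample size does.

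The sample size and the entry comparison are not affected. The plan should be changed because the claim of predictive value rests on this objective and the needed data are already being collected.

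**What to change.** - Keep the two-group tests and state that they apply to the entry comparison.
- For the predictive objective, model activity by 6 months (global for JSLE, renal for adult SLE) on entry HCQ level in all patients, adjusted for entry activity: entry SLEDAI-2K for JSLE, entry renal activity for adults. State how the 3-monthly assessments define the outcome.
- Add an analysis of new activity in patients inactive at entry, with an ROC area and confidence interval. If 1000 ng/mL is to serve as a cut-off, name it in advance and report sensitivity and specificity with exact confidence intervals.
- State the expected number of new events. For the restricted JSLE analysis, use HCQ level alone or a penalised model, and say beforehand that it will be imprecise.

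The cost is a paragraph in the statistical plan. Entry HCQ and 3-monthly activity are already planned, so no visits, samples or patients are added. The downside is that the restricted analysis rests on few events, and in JSLE it may be inconclusive.

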In the proposed project, there is a special need to obtain high accuracy due to the toxicity of the drugs studied and the need for precise adjustment of therapeutic levels. In the logistics aspect, the methodology allows simplification in the procedures of extraction of the analytes and reduction in the acquisition time of bioanalytical data. Consequently, with smaller turn-around times there is an increase in processing capacity in the analytical stage, enabling the analysis of hundreds/thousands of samples in the time frame compatible with the proposed study. The multiplexing capacity of the determinations is an unattainable aspect regarding other quantification methods, however using HPLC/MS-MS in this project will allow the determination of the intact drug and its metabolites in a single acquisition, generating more comprehensive results that could reveal in more depth the therapeutic dynamics.

The implementation of this methodology for research and routine in our center, with the necessary training of human resources, will allow the standardization and availability of this advanced technology for other multidisciplinary projects in various areas of science. In addition, drug concentrations obtain from patients in this study will be used to establish pharmacokinetic-pharmacodynamic models for GC, thalidomide and hydroxychloroquine use in patients with SLE. Pharmacokinetic-pharmacodynamic modeling is a technique that combines two important aspects in medical therapy: pharmacokinetics and pharmacodynamics. This integration is done in a series of mathematical expressions that allows the description of the duration of the therapeutic effect in relation to the dose administered (Poggi JC et al., 2006). This thematic project will be divided into four sections with their respective subprojects, according to the medications that will be studied:

1. hydroxychloroquine;
2. thalidomide.

Project 1: HYDROXYCHLOROQUINE (1A, 1B and 1C)

Evaluation of the relevance of determining blood levels of hydroxychloroquine and its metabolites in rheumatologic autoimmune diseases: safety/efficacy of therapy, disease activity, adherence to therapy and cost-effectiveness

TITLE OF THE SUBPROJECT

Correlation of blood levels of hydroxychloroquine (HCQ) with the indices of disease activity and adherence to therapy in a cross-sectional study diseases Systemic lupus erythematosus (SLE), and Juvenile systemic lupus erythematosus (JSLE).

Background

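### Subproject 1A promises a correlation of HCQ level with activity indices, but for JSLE it plans only an active-versus-inactive comparison at an undefended SLEDAI-2K cut of 6; add an analysis of the score itself

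*Combined protocol and SAP*

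**What the plan says.** The title of subproject 1A announces a "Correlation of blood levels of hydroxychloroquine (HCQ) with the indices of disease activity and adherence to therapy in a cross-sectional study". The primary objective concerns HCQ levels and their "possible relevance on disease activity in JSLE and renal adult SLE to inclusion and 6 months following inclusion".

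Under Study design, the activity indices are assessed every 3 months. For SLE and JSLE the index is SLEDAI-2K, with "active disease randomly defined as SLEDAI-2K" of at least 6. The citation beside it is for the index; no reason is given for the value 6. The outcomes text of subproject 1B gives the score's range as 0 to 105.

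The analysis text, which follows the sample size in the 1A statistical plan, is one sentence. It opens: "The groups of patients with and without disease activity will be compared for categorical variables by Fisher's exact test". The rest of that sentence assigns t or Mann-Whitney tests to the quantitative variables. HCQ level is one of these, so its planned analysis is such a test between activity groups. No correlation or regression is named.

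The sample size paragraph sets "95% confidence interval, α error of 5%; power of 80" per cent, and "mean HCQ concentration in active patients: 694 ± 448 ng/mL" against 1079 ± 526 ng/mL in inactive patients. It gives an aggregate SD of 532 ng/mL and 10% loss. It expects 35 active among 103 JSLE patients (34%), and 33 with active renal disease among 206 adults (16%).

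**The concern.** The titled question is how HCQ level varies with the activity indices. For JSLE the stated analysis answers a narrower one: whether mean level differs between patients above and below a single cut. A patient scoring 0 is pooled with one scoring 4, and one scoring 6 with one scoring 20. Any gradient within the two groups is ignored, and the result depends on a threshold that the plan does not defend. The stake is precision, and an answer to the question in the title, from scores that are collected anyway.

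**Working it through.** **1. The plan's own figures.** The difference is 1079 − 694 = 385 ng/mL. With SD 532, two-sided 5% (sidedness is not stated; assumed), 80% power and equal groups, the normal formula gives 2 × (1.96 + 0.842)² × (532/385)² = 29.97, so 30 per group; the t-based solution is 31.
- JSLE: 31/0.9 = 34.4, so 35 active; 35/0.34 = 102.9, so 103.
- Adults: 30 × 1.1 = 33; 33/0.16 = 206.

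Both stated sizes reproduce, with slightly different rounding. The active group was sized as if the groups were equal. In JSLE the inactive group is about twice as large (68), so actual power exceeds 80%.

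**2. Which SD.** A pooled within-group SD must lie between 448 and 526, so 532 cannot be one. At 34% active:
- within-group: √(0.34 × 448² + 0.66 × 526²) = √250,845 ≈ 501
- total: √(250,845 + 0.34 × 0.66 × 385²) ≈ 533

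The stated 532 is close to the total SD. I therefore show both 501 and 532.

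**3. Information kept by the split.** Assume that an underlying normal activity trait is linearly related to HCQ, and that the 34% active are those scoring 6 or more. The cut is then at z = 0.412, where the normal density is 0.366. The efficiency of the split is 0.366²/(0.34 × 0.66) = 0.60, a 40% loss against a fully continuous score.

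With d = 385/532 = 0.724, the point-biserial r is d/√(d² + 1/(0.34 × 0.66)) = 0.324, and the underlying r is 0.324/√0.598 = 0.419. With SD 501, d = 0.769 and the two values are 0.342 and 0.442.

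**4. Power for JSLE.** The t-test figures are exact (noncentral t). The continuous-score column uses the Fisher z approximation. The coarse-score column is simulated (20,000 runs) with an assumed SLEDAI-like distribution: 30% zeros and values 0, 2, 4, 6, 8, 10, 14 and 20. The second row of each pair is after 10% loss.

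| SD | n (active v inactive) | t-test at the cut | Spearman, coarse score | Correlation, continuous score |
|---|---|---|---|---|
| 532 | 103 (35 v 68) | 93.1% | 98.3% | 99.4% |
| 532 | 93 (32 v 61) | 90.7% | 97.5% | 98.9% |
| 501 | 103 (35 v 68) | 95.5% | 99.1% | 99.7% |
| 501 | 93 (32 v 61) | 93.6% | 98.7% | 99.5% |

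The gain is about 4 to 7 points with the coarse score and 4 to 8 with a continuous one.

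For the coarse score, relative information is ((1.96 + z of the t-test power)/(1.96 + z of the Spearman power))², where z is the normal quantile. It comes to about 0.69 to 0.72, a loss near 30%.

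**5. The opposite case.** Suppose HCQ differs only as a step at the cut, with means 694 and 1079 and SDs 448 and 526. Simulation (4,000 runs) then gives 96% for the t-test against 85% for Spearman at n = 103, and 94% against 81% at n = 93. The two-group test is the better one here.

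**The case against.** The best defence is that the two-group contrast is legitimate and adequately powered. The primary objective asks about the relevance of HCQ level to disease activity, and an active-versus-inactive comparison answers that in a form that clinicians can read. It is also the quantity on which the sample size rests, and HCQ itself stays continuous. The sources give only a two-group difference; nothing in the documents shows a gradient across the score, and under a pure step the score analysis loses. All of this stands. It is why the two-group comparison should be kept and the loss given as conditional.

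Three stronger readings are tempting, and the documents do not support them.
- A reader might infer that all of 1A hangs on the SLEDAI-2K cut. The 206 adults are sized on active renal disease, so the point concerns only the 103 JSLE patients.
- A reader might infer that 1A is underpowered. The planned t-test has about 91% or more under the plan's own figures.
- A reader might take the 40% loss as established. It holds for a continuous, bivariate-normal score; with a coarse score it is nearer 30%, and under a step the advantage reverses.

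The wording about a randomly defined cut is probably a translation of arbitrarily. It shows that no justification is given, not that 6 is wrong.

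What survives is the mismatch itself: the title promises a correlation with the indices, and no correlation is planned.

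**Conclusion.** The point holds as a modest, inexpensive improvement for the JSLE part of 1A. That the title and the stated analysis do not match needs no modelling assumption. The size of the loss does: roughly 30 to 40% of the information and about 4 to 8 points of power (about 91 to 96% against 98 to 99%). This range rests on a graded relation, an approximately normal underlying trait, a within-group SD of 501 to 532, 93 to 103 patients, and the 34% active being those who score 6 or more. The statistical plan says only that 34% have active disease and does not tie that figure to the cut. The case for change is that the titled question goes unanswered and precision is given up; it is not a failure of power or validity.

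**What to change.** In the 1A statistical plan, specify for JSLE at inclusion a Spearman correlation of HCQ blood level with the SLEDAI-2K score, with a 95% interval, as the analysis that answers the titled question. A regression would also serve; choose one before the data are examined. Keep the comparison of SLEDAI-2K 6 or more against below 6, on which the sample size was based, and report it beside the correlation.

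This costs SAP wording and one more analysis, with no new patients, visits or assays. The downside is lower power for the score analysis under a pure step relation, which the retained two-group comparison covers.

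### Subproject 1A: Student's t pools unequal planning SDs over groups of 33 and 173, giving an adult interval about 9.5% wider than Welch's and a conservative test

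*Combined protocol and SAP*

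**What the plan says.** The statistical plan of Subproject 1A compares patients with and without disease activity by Fisher's exact test for categorical variables and, "for quantitative variables, by student and mann-whitney t tests, when applicable". It names no unequal-variance test, no scale of analysis and no rule for choosing between the two tests.

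The sample size paragraph bases the study on the HCQ level by activity status: "mean HCQ concentration in active patients: 694 ± 448 ng/mL; mean HCQ concentration in inactive patients: 1079 ± 526 ng/mL". It uses one aggregate SD of 532 ng/mL, a 5% α error, 80% power and 10% loss.

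For adults, "16% of SLE patients in our outpatient clinic present active renal disease", and so "we expect 33 patients with renal activity out of the 206 patients". That leaves 206 − 33 = 173 without renal activity. For JSLE it expects 35 active of 103, leaving 68.

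**The concern.** Student's t assumes one common variance. It tolerates unequal spread when the groups are of similar size, and unequal sizes when the spreads are similar. The planning figures of 1A have neither. The pooled variance is dominated by the large inactive group, and its SD is then applied to the small active group.

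When the small group has the smaller SD, as here in ng/mL, the pooled standard error is too large: the interval is wider than it need be and the real error rate falls below 5%. When the small group has the larger spread, the opposite happens. At stake is the accuracy of the interval and p-value for the comparison on which 1A was sized.

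**Working it through.** **Inputs** (1A, sample size paragraph): means 694 and 1079 ng/mL (difference 385), SDs 448 and 526, sizing SD 532, α 0.05 (two-sided assumed; the plan does not say), power 0.80. Group sizes are 33 v 173 and 35 v 68; 173 and 68 are obtained by subtraction.

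**The plan's own sample size**
- n per group = 2 × (1.960 + 0.842)² × 532² / 385² = 29.97, so 30.
- Adults: 30 × 1.1 = 33, and 33 / 0.16 = 206.
- JSLE: the t-based n is 31; 31 / 0.9 = 34.4, so 35; and 35 / 0.34 = 103.

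Both stated totals can be reproduced, so the inputs are read correctly.

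**Standard errors in ng/mL**
- Adults, pooled SD = √[(32 × 448² + 172 × 526²) / 204] = 514.5. Student SE = 514.5 × √(1/33 + 1/173) = 97.7.
- Adults, Welch SE = √(448²/33 + 526²/173) = 87.6. Ratio 97.7 / 87.6 = 1.115.
- JSLE, pooled SD = 501.1. Student SE = 501.1 × √(1/35 + 1/68) = 104.2; Welch SE = √(448²/35 + 526²/68) = 99.0. Ratio 1.053.

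**95% half-widths, each with its own degrees of freedom**
- Adults: Student 1.972 × 97.74 = 192.7 (204 df); Welch 2.008 × 87.64 = 176.0 (about 50 df). Ratio 1.095.
- JSLE: Student 206.8 (101 df); Welch 197.1 (about 79 df). Ratio 1.049.

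**Real type I error at nominal 5%**, approximately 2 × [1 − Φ(1.96 × SE ratio)]
- Adults: 2 × [1 − Φ(2.186)] = 2.9%. Simulation with normal data and equal means: Student 2.9%, Mann-Whitney 3.6%, Welch 4.9%.
- JSLE: 3.9% by formula. Simulation: Student 4.1%, Mann-Whitney 4.4%, Welch 5.1%.

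**Power at 385 ng/mL** (simulated, normal data)
- Adults: Student 98.5%, Welch 99.1%.
- JSLE: Student 96.2%, Welch 97.0%.
- With 10% removed as losses, adults (30 v 155) have 97.6% with Student and JSLE (32 v 61) about 94.6%.

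**Conditional check on the log scale** (lognormal shape assumed; not in the plan)
- Log SD = √ln(1 + CV²). Active: CV 448/694 = 0.646, log SD 0.590. Inactive: CV 526/1079 = 0.487, log SD 0.462. The small group now has the larger spread.
- Adults: Student SE 0.0920, Welch SE 0.1086, ratio 0.847. Simulated error: Student 9.6%, Mann-Whitney 7.4%, Welch 5.1%.
- JSLE: ratio 0.925. Simulated error: Student 7.1%, Mann-Whitney 6.1%, Welch 5.0%.

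**The case against.** The case for leaving the plan alone has four parts.

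- **The test errs on the safe side.** In ng/mL, the scale of the planning figures, false positives fall below 5%, and at the planned difference the choice of test hardly alters the chance of a positive result. This stands, and it is why the point is minor.
- **The SDs are planning values.** By 1A's own background, the cited adult study assessed global rather than renal activity, and there were no juvenile data. The variance ratio is 526²/448² = 1.38; at 33 v 173 an F test on exactly these SDs gives p = 0.28. This also stands: the figures do not prove that 1A's groups will differ in spread. But Welch costs almost nothing if they do not, so uncertainty is no reason to keep the pooled form.
- **The plan's phrase about applicability leaves room.** It is undefined and might be taken to cover an unequal-variance t-test. As written, though, it offers two named tests, and Mann-Whitney does not hold exactly 5% under unequal spread either.
- **A log analysis changes what is estimated.** It moves from the ng/mL difference used for sizing to a ratio of geometric means and needs a rule for undetectable levels. This is a fair reason not to make it primary.

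Two stronger readings are tempting. A reader might take the 11.5% excess in the standard error as the excess width of the interval; it is 9.5%, because Welch has fewer degrees of freedom. A reader might also infer that 1A carries about a 10% false-positive rate. That figure needs a roughly lognormal shape and pooled Student's t on logged levels, and the plan states neither. The shape is plausible, since a normal curve with mean 694 and SD 448 puts about 6% of values below zero, but plausibility does not make it the planned analysis.

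**Conclusion.** The concern holds as a small inefficiency. With the plan's SDs and expected group sizes, Student's t gives an adult interval about 9.5% wider than Welch's (193 v 176 ng/mL) with a real error of about 3%, and a JSLE interval about 5% wider with an error of about 4%. It does not threaten the planned comparison: power at 385 ng/mL is above 95% in both populations at the planned sizes, and about 94.6% in JSLE if the 10% loss is realised.

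This rests on SDs of 448 and 526 ng/mL holding when the means are equal. If the SD-to-mean ratios (65% and 49%) carried over instead, with a lognormal shape, the order of the spreads would reverse. Simulated adult error is then 9.6% for Student on logged levels, and 10.0% even in ng/mL, where Welch gives 6.3%. The documents do not support choosing that scenario. It shows that the direction of Student's error depends on things the plan leaves open, while Welch stays closer to 5% throughout.

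**What to change.** In the statistical analysis paragraph of Subproject 1A, replace Student's t with Welch's unequal-variance t-test for the primary comparison of HCQ level, separately in adult SLE (renal activity) and in JSLE. Report the difference in mean level in ng/mL with its 95% CI. A log-scale analysis can be added as a pre-specified sensitivity analysis, with a fixed rule for undetectable levels.

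The cost is one sentence, with no new data and no change to the sample size. If the spreads prove equal, about 1 percentage point of power or less is lost at the planned difference: with a common SD of 532 ng/mL, simulated adult power is 96.7% with Student and 96.2% with Welch.
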